Evaluation of Three Non-invasive Analgesic Techniques in Pain Prevention During Injections

Clinicaltrials.gov - NCT03974633

Date of last Statistical Analysis Plan edition: 19/08/2019

- Performed in order to adapt the protocol to the requirements of registration at clinicaltrials.gov

Date of previous Statistical Analysis Plan: 08/06/2018

Protocol version 2.0

Person writing SAP: [name]

SAP Contributors: [name]

Senior statistician: [name] (blind researcher)

Principal Investigator: [name]

Investigators participating in the practical part of the study:

- [name]
- [name]
- [name]
- [name]

Background

The application of injectable substances, whether local anesthetics, vaccines, drugs or cosmetics, can cause significant pain and discomfort. There exists a wide range of variables that may influence the subjective experience of each patient during the performance of an injection, like the type of substance utilized, the volume of liquid infiltrated, the anatomic location, or whether a non-invasive anesthetic technique is utilized (1).

As regards traditionally used non-invasive analgesic techniques for pain control during injections, there are a limited amount of clinical trials that provide an adequate level of evidence in this field (1). Some studies claim to have proven the efficacy of cold, anesthetic creams or vibration for pain control during injections (2). Notwithstanding, these studies have generally focused in comparing only the studied analgesic technique with a control group, instead of comparing anesthetic techniques among themselves (2). Furthermore, it is even scarcer the amount of studies focused in the field of cosmetic subcutaneous injections; whereas most of the reported studies have been performed in the context of anesthetic injection in odontology, intravitreal injections, or blood sample collection in pediatric population (3).

The use of cold for pain control during injection has been traditionally utilized in different contexts. Notwithstanding, scientific evidence in favor of the use of cold as an analgesic agent in the context of injections is scarce, and has a low level of evidence (4). The mechanisms through which cold is considered to elevate pain threshold are: an alteration of nerve conduction, reduction of muscle spasms and prevention of tissue edema (4-6).

The application of topical anesthetic cream is frequently used for minimizing pain caused by injections (3). The main disadvantage of this method is the time required for the anesthetic effect to start. Different studies have shown that penetration depth of the anesthetic effect is of 3mm after 30-60 minutes, and 5mm after 90-120 minutes (7,8). Many authors reported better results in pain control with the use of this type of substances than with placebo (9-13). Notwithstanding, most of those studies were focused in the use of topical anesthetics in oral mucosa prior to anesthetic injection in odontology procedures, and most of them included reduced samples (lower than 50 subjects) (9,10,14-18). There is also a relevant amount of studies that did not find any statistically significant differences in terms of pain control between control and intervention groups (14-19).

Vibration analgesia was first described in 1984 by Reed et al (20). It is the non-invasive method that has been studied less in classic literature, although in the last 10 years its interest has grown significantly, with the apparition of new studies in different clinical contexts, and with results that generally favor its use (21-25). The studies that have reported an improvement in pain control have been performed in the field of odontology (21), infiltration of local anesthetics in children (22), keloid infiltration (23), botulinum toxin injection (24), and hyaluronic acid injection for lip filling (25). Notwithstanding, other studies have reported unfavorable results for this analgesic method, in the field of venipuncture in children, and anesthetic injections in odontology (26-28). All authors agree that the amount of studies focused in this type of anesthetic method is scarce, and that more studies with a higher level of evidence are required in order to evaluate its real utility (20-31).

References


Objective

In this clinical trial, we evaluated the effectivity of three non-invasive analgesic techniques (cold, anesthetic cream and vibration), including a control zone, in 100 healthy individuals, by performing subcutaneous forehead injections of 0,1ml physiologic saline.

Hypotheses

[figure not shown]
Any of the analgesic methods improves pain control respect to not utilizing any of them.

Our second aim is to evaluate if any of the analgesic methods evaluated achieves a better pain control than the others.

Randomization details

The sequence of infiltration zones of each subject was randomized through simple randomization, performed by the statistic department of the Medical Research Institute Hospital La Fe.

CONSORT Flow Diagram

Interim analysis

Performed by: [name]

Date: 16/03/2019

An interim analysis was performed when 50 subjects had already been recruited. A sample size of 46 subjects (184 interventions) was estimated, assuming a variance in the values of the control zone of 2,69, with a precision of 1, confidence level of 95%, and statistical power of 0,9.

No modifications were performed to the protocol after the interim analysis.

Guidelines for stopping study early: None

Date of final analysis: 30/04/2019

No protocol deviations were detected

Intervention adherence was not necessary as no follow-up was required

Population analyzed

From the 100 healthy subjects included in the study, 61 were females and 39 males. The average age was 39,71 (sd 13,22).

Exclusion criteria

- Chronic pain syndromes/conditions
- Receiving opioid analgesics and sedatives
- Extreme sensitivity to cold
- Allergy to components of the anesthetic cream EMLA (eutectic mixture of lidocaine; 2,5% lidocaine and prilocaine 2,5%)
- Inability to understand the visual analogic scale

Inclusion criteria

Every subject that did not meet any of the exclusion criteria, and signed the informed consent, was included in the study

Recruitment strategy

Adult employees and volunteers at The University and Polytechnic Hospital La Fe that understood the study and signed the informed consent were eligible for participation.

We did not have any case of **withdrawal** from the study

Material and methods

This study is a randomized, controlled, simple-blind clinical trial, and it has been approved by the Ethics Committee of the Medical Research Institute Hospital La Fe. The study included 100 healthy volunteers, and it was performed at the University and Polytechnic Hospital La Fe, Valencia.

The procedures of the study consisted in the sequential performance of four injections of 0,1mL of physiologic saline (0,9%NaCl) in the forehead of each subject, 2cm above the eyebrows, with a 29G needle, after applying each one of the non-invasive analgesic methods studied in the trial, except for the control zone. The anesthetic method utilized in each part of the forehead of each patient was randomized through simple randomization. Injections always started from the right side of the forehead to the left. The non-invasive analgesic methods utilized were:

- Control zone (A): None
- Vibration (B): Application of the vibrating device on the skin below the injection site, before and during injection.
- Cold (C): Application of a bag of 50mL of frozen physiologic saline covered with a plastic glove on the injection site for 50 seconds prior to performing the injection.
- Anesthetic cream (D): Application of a uniform thickness of 2mm of the anesthetic cream EMLA covered with an adhesive transparent plastic dressing for 30 minutes, before injection.

Results were evaluated through surveys that included demographic data (initials, gender, age), a Visual Analogic Scale (VAS) with a maximum value of 10 and minimum of 0 for pain evaluation of each of the four injected zones of each subject. Also, two direct questions were included, one with the aim of determining the preferred method for each subject for future injections (“Which anesthetic technique would you prefer if you had to be injected again?”), and another to report discomfort related to the application of any of the anesthetic procedures (“Did any of the anesthetic methods cause you pain or discomfort?”)

An interim analysis was performed when 50 subjects had already been recruited. A sample size of 46 subjects (184 interventions) was estimated, assuming a variance in the values of the control zone of 2,69, with a precision of 1, confidence level of 95%, and statistical power of 0,9. The statistical study included a Friedman test for evaluating the existence of differences between the average results of each different anesthetic method and control zones, and to evaluate the existence of differences in pain referred depending on the injection order, or the side of the forehead injected (central or lateral). After finding statistically significant differences between average pain referred with different techniques, paired comparisons were performed between each non-invasive anesthetic method with a Wilcoxon test. For comparison of average pain according to subject gender, a Mann-Whitney U test was utilized. Statistical analysis was performed by a researcher that did not participate in the practical part of the study ([name]) utilizing the software SPSS.

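### Balance of the techniques over the four injection positions was not guaranteed, and the technique comparisons make no adjustment for position; a position-adjusted analysis would recover the precision this may cost

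*Combined protocol and SAP*

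**What the plan says.** Two places describe the allocation. Randomization details: "The sequence of infiltration zones of each subject was randomized through simple randomization". Material and methods: "The anesthetic method utilized in each part of the forehead of each patient was randomized through simple randomization". Neither mentions a block, a Latin square or any other balancing restriction, and no table of technique by position is given.

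Material and methods also describes "the sequential performance of four injections of 0,1mL of physiologic saline" and adds: "Injections always started from the right side of the forehead to the left". Forehead site and injection order are therefore one four-level factor, called position here. The central or lateral grouping is a coarser version of it.

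The last paragraph of Material and methods gives the analysis. A Friedman test compares the techniques and control, and is also used for injection order and for central or lateral site. Pairwise Wilcoxon tests between techniques follow. No position term is described for any technique comparison.

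**The concern.** If pain depends on position (anxiety at the first injection, sensitisation, site), a technique that happens to fall more often in a painful position scores worse for that reason alone. Simple randomisation leaves this to chance, and the described tests do not remove it. Position must be known for each score, since order and site are tested, but that information is not carried into the technique comparison. The second aim is the most exposed, because differences between active techniques are likely to be smaller than differences from control.

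**Working it through.** **Inputs from the documents.** "The study included 100 healthy volunteers"; four positions; simple randomisation; "assuming a variance in the values of the control zone of 2,69"; "with a precision of 1" (one VAS point).

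**Assumptions.** The documents give no position effect and no within-subject correlation (rho). I take a position effect of 1 point, with 0.5 and 2 as a range, and rho = 0.3, 0.5, 0.7. I apply the control-zone variance to all four conditions.

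**The plan's own figure.** "A sample size of 46 subjects (184 interventions) was estimated". For two independent means, n = 2 × 2.69 × (z_alpha + z_power)² / 1².
- One-sided 5%, power 0.9: 5.38 × (1.645 + 1.282)² = 46.07, so 46, and 46 × 4 = 184. This reproduces the figure.
- Two-sided: 56.5, so 57. This does not.

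Sidedness is not stated, which is a separate matter. Position does not enter the calculation either way.

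**Expected imbalance at N = 100.** The count of a technique in a position has mean 25 and SD √(100 × 0.25 × 0.75) = 4.33. In 200,000 simulated lists drawn uniformly from the 24 orders:
- A single cell had a 95% range of 17 to 34.
- Some cell was off by at least 5 subjects in 98% of lists, and by at least 10 in 31%.
- The gap between the most and least frequent technique in first position had median 10 and 95th percentile 18, and was 15 or more in 17% of lists.
- Exact balance never occurred.

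**Chance shift in a technique difference.** For two techniques in different random positions, the variance of the difference in position effects is 2S², where S² is the variance of the four effects (divisor 3).
- First-injection effect (1, 0, 0, 0): S² = 0.75/3 = 0.25. SD of the shift = √(0.5/100) = 0.071.
- Linear drift (0, 1/3, 2/3, 1): S² = 0.5556/3 = 0.1852. SD of the shift = √(0.3704/100) = 0.061.

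**Share of the variance.** Without position effects, the variance of a paired mean difference is 2 × 2.69 × (1 − rho)/100.

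| rho | Variance | First-injection share | Linear-drift share |
|---|---|---|---|
| 0.3 | 0.03766 | 0.00500/0.04266 = 12% | 0.00370/0.04136 = 9% |
| 0.5 | 0.02690 | 0.00500/0.03190 = 16% | 0.00370/0.03060 = 12% |
| 0.7 | 0.01614 | 0.00500/0.02114 = 24% | 0.00370/0.01984 = 19% |

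The shift scales with the position effect. At rho = 0.5 the share is 3 to 4% for a 0.5-point effect and 36 to 43% for a 2-point effect.

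**Effect on the tests.** Simulated normal scores, rho = 0.5, linear drift, N = 100, 2,000 trials per scenario; power is for a true difference of 0.7.

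| Drift | List | Wilcoxon type I | Wilcoxon power | SE unadjusted | SE adjusted |
|---|---|---|---|---|---|
| 1 | Simple | 0.053 | 0.973 | 0.18 | 0.17 |
| 1 | Williams | 0.044 | 0.981 | 0.16–0.17 | 0.16–0.17 |
| 2 | Simple | 0.052 | 0.914 | 0.20–0.21 | 0.163–0.166 |
| 2 | Williams | 0.018 | 0.960 | 0.163–0.165 | 0.163–0.165 |

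Adjusting for position on the simple list gives nearly the same standard error as a balanced list.

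**The case against.** The strongest reply is that simple randomisation of order is a valid design. It is balanced in expectation, and the extra scatter from position is part of the within-subject differences on which the Wilcoxon test works, so its type I error stays near 0.05. That stands. A reader might infer from the lack of balancing that the technique comparison is biased, or that the techniques were in fact badly distributed. The documents support neither: realised counts are not reported, and chance imbalance is sampling variability. Nor does testing for order and site show that the investigators expected a position effect; it shows only that they checked for one.

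A second reply is that a balanced list alone would have gained little. This also stands. With a 1-point first-injection effect, N = 100 and rho = 0.3/0.5/0.7, simulated Wilcoxon power for a true difference of 0.5 is 0.66/0.77/0.91 with simple randomisation and 0.66/0.79/0.94 with a Williams list. For a difference of 1 it is at or near 1 with either. Under no difference, the Wilcoxon test on the balanced list rejects in only 0.037/0.032/0.025 of trials, so it becomes conservative. Balance pays off fully only with a position term.

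Third, the list can no longer be changed. The final analysis is dated 30/04/2019 and this SAP edition 19/08/2019. That is right, and it moves the useful change from the list to the analysis. It does not remove the point, because the adjustment needs only data already collected.

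**Conclusion.** The point holds as a loss of precision, not as a failure of validity. Balance over position was not guaranteed, exact balance by chance at N = 100 is practically impossible, and the technique comparisons take no account of position. Under an assumed 1-point effect, chance imbalance makes up about 12/16/24% (first-injection effect) or 9/12/19% (linear drift) of the variance of a technique difference at rho = 0.3/0.5/0.7. The chance shift itself is small: an SD of 0.06 to 0.07 against a planned precision of 1 point. With no position effect there is no loss; with a 2-point effect it is substantial.

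These sizes rest on the assumed position effect and correlation, on a common variance of 2.69, and on additive effects with normal scores rather than a bounded VAS. This is an inexpensive improvement to the analysis, not grounds for rejecting the results.

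**What to change.** For the present data:
- Report the 4 × 4 table of technique by position counts.
- Repeat the technique comparison with position as a factor, alongside the planned Wilcoxon tests. An example is a linear mixed model for VAS with technique and four-level position as fixed effects and subject as a random effect. Report adjusted differences with confidence intervals.
- Label this as an added sensitivity analysis, since it comes after the final analysis.

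The cost is a little more analysis work and reliance on an additive linear model for a bounded score. No new data are needed.

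For any repeat or extension, generate the list as a Williams square: four sequences of 25 subjects at N = 100, in random order. Each technique then falls 25 times in each position and directly follows each other technique 25 times, with no added subjects or procedures. Exact balance needs a multiple of 4, so 46 would become 44 or 48. Specify the position term with the list, because the unadjusted Wilcoxon test is conservative on a balanced list when position matters.

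### Does the unexplained basis of the 46-subject estimate, and the lack of a planned confidence interval for the paired differences, call for a change to the plan?

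*Combined protocol and SAP*

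**What the plan says.** The Interim analysis section and the statistical paragraph of Material and methods carry the same sizing sentence. It reads "A sample size of 46 subjects (184 interventions) was estimated, assuming a variance in the values of the control zone of 2,69", and continues "with a precision of 1, confidence level of 95%, and statistical power of 0,9". The outcome is "a Visual Analogic Scale (VAS) with a maximum value of 10 and minimum of 0 for pain evaluation", scored once for each of the four forehead zones of every subject. The number studied is stated separately: "The study included 100 healthy volunteers".

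The Hypotheses section has a first, directional statement, "Any of the analgesic methods improves pain control respect to not utilizing any of them", and a second: "Our second aim is to evaluate if any of the analgesic methods evaluated achieves a better pain control than the others".

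For the analysis, Material and methods names a "Friedman test for evaluating the existence of differences between the average results of each different anesthetic method and control zones". If that test is significant, "paired comparisons were performed between each non-invasive anesthetic method with a Wilcoxon test". A Mann-Whitney U test serves the comparison by gender. The text speaks of average pain by technique. It does not mention a paired difference or a confidence interval, and the value 1 does not appear again.

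**The concern.** Two things look wrong on a first reading.

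- **The estimate cannot be traced.** All four injections are given to the same person and the pairwise test is a paired one, so the variance that matters is that of the within-subject difference. The plan gives only the control-zone variance, and it states neither the sidedness nor the formula. Different standard choices lead to quite different numbers from the same inputs.
- **The target of 1 disappears.** If it was the difference the trial was sized to detect, one expects the results to be read against it. With 100 subjects instead of 46, a difference well under 1 point can be significant, and a technique could be called better on the strength of it. In the other direction, a non-significant pair of techniques might be reported only as showing no difference, when an interval could often rule out a difference as large as 1 point.

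At stake is how the second aim is read, and possibly confidence in the size of the trial.

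**Working it through.** **Inputs from the documents.** Control-zone variance 2.69; precision 1; confidence 95%; power 0.9; estimate 46; number studied 100.

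**Assumptions, not in the documents.** The 1 is in VAS points; the variance is 2.69 in every zone; the within-subject correlation ρ is 0, 0.3 or 0.5; the tests are two-sided at 5%.

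**Step 1: reproduce the 46.** Normal quantiles: 1.6449 (one-sided 5%), 1.96 (two-sided 5%), 1.2816 (power 0.9).

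| Reading | Formula | Result |
|---|---|---|
| One-sided, independent groups (or paired, ρ = 0) | 2 × 2.69 × (1.6449 + 1.2816)² | 46.07 |
| Two-sided, independent groups | 2 × 2.69 × (1.96 + 1.2816)² | 56.5 |
| Two-sided, 2.69 as variance of the difference | 2.69 × (1.96 + 1.2816)² | 28.3 |
| Precision as half-width, one mean | 1.96² × 2.69 | 10.3, so 11 |
| Precision as half-width, difference of two means | 1.96² × 2 × 2.69 | 20.7, so 21 |

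The first row matches 46 if rounded to the nearest whole number, and 46 × 4 = 184 interventions. A two-sided paired formula also gives 46, but only at ρ of about 0.19 (1 − 46/56.5), which is not stated. The half-width readings do not give 46 and would leave the stated power without a role, so the 1 is most plausibly a difference to detect. That remains an inference.

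**Step 2: is the trial large enough?** Take the less favourable two-sided reading at ρ = 0. The SD of the difference is √(2 × 2.69) = 2.319. With 100 pairs the standard error is 0.232, and power for 1 point is Φ(1/0.232 − 1.96) = 0.99. Bonferroni correction over six pairs would still leave 0.95. Both figures are for a single pair and leave out the preliminary Friedman test. With 46 pairs the uncorrected figure would be 0.83.

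**Step 3: how small a difference can be significant?** SD of differences = √(2 × 2.69 × (1 − ρ)); half-width at N = 100 is 1.9842 × SD/10.

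| ρ | SD of differences | 95% half-width | Power for 0.5 point, paired t alone | Friedman, then Wilcoxon |
|---|---|---|---|---|
| 0 | 2.32 | 0.46 | 0.57 | about 0.38 |
| 0.3 | 1.94 | 0.39 | 0.72 | about 0.54 to 0.57 |
| 0.5 | 1.64 | 0.33 | 0.86 | about 0.71 |

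The last column follows the plan's sequence. It was simulated with one technique half a point away from the other three zones, scores in steps of 0.1 clipped to 0–10 and a control mean of 4. The range at ρ = 0.3 reflects two simulation runs. Ignoring the Friedman step overstates how readily the procedure reacts to half a point.

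**Step 4: non-significant pairs.** If a paired t interval includes zero, its far end lies within twice the half-width: 0.92, 0.77 or 0.65 points. It excludes 1 point whenever the SD of differences is below 10/(2 × 1.9842) = 2.52. This usually holds but is not guaranteed. If a technique zone had 1.5 times the control variance, then at ρ = 0 the SD would be √(2.69 × 2.5) = 2.59.

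**The case for a change.** The best case for a change runs as follows. The plan supplies its own benchmark and then does not use it. Significance can arrive at less than half a point, and an interval would show whether a significant result is small or a null result informative. The remedy would be one completed sentence and six rows of results from data already in hand.

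Much of this stands. The omissions are on the page and are not the result of redaction, the arithmetic is right, and intervals are good reporting practice. Three parts do not carry over into a change of plan.

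- The documents call the 1 a precision, give it no unit and never present it as the smallest worthwhile benefit. Neither hypothesis is defined by it. Requiring each result to be judged against it would give it a role the plan did not.
- The size of an effect need not be hidden. The plan works with average pain by technique on a 0–10 scale, so if those averages are reported a reader can see how far apart they are. What would be missing is their uncertainty. A brief list of tests that is silent on intervals does not show that none will be reported.
- The sizing sentence concerns 46 subjects, and the final analysis, dated 30/04/2019, covers 100. Explaining the 46 in more detail cannot alter that analysis.

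**Conclusion.** No change to the plan follows. The sizing sentence lacks detail, but one standard formula reproduces its figure. The number studied is more than twice the estimate, and the trial is not shown to be underpowered on any of the assumptions tried. Filling in the test, sidedness and variance would document the calculation without altering any result.

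The missing interval is a gap that an analyst would sensibly fill at the reporting stage. The Friedman, Wilcoxon and Mann-Whitney tests address the stated hypotheses and remain valid without it. Differences under 1 point can be declared significant: for half a point, about 0.38, 0.54 to 0.57 and 0.71 of the time at correlations 0, 0.3 and 0.5 under the planned two-step rule. This is a caution about describing effect size, not an error in the tests. A non-significant pair would normally, though not always, have a 95% t interval that excludes 1 point.

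These sizes rest on equal variances of 2.69, the assumed correlations, and reading the precision of 1 as a 1-point VAS difference. No interval matched to the Wilcoxon test was computed. The conclusion that no change is needed does not depend on the exact values.

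### Does the plan have to change because the subjects who score their own pain appear unmasked and no interval is named?

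*Combined protocol and SAP*

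**What the plan says.** The opening of Material and methods states: "This study is a randomized, controlled, simple-blind clinical trial". It does not say who was blinded. Two other places bear on this. The list of roles on the title page marks the senior statistician as "blind researcher", and the statistical paragraph of Material and methods adds: "Statistical analysis was performed by a researcher that did not participate in the practical part of the study". Nothing says that subjects were masked.

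Each subject receives all four conditions. The control condition is "Control zone (A): None". The other three are a vibrating device, a frozen saline bag held on for 50 seconds, and EMLA cream under a dressing for 30 minutes. No sham device, placebo cream or unfrozen bag is described. The subject gives a 0 to 10 VAS score for each zone and is asked "Which anesthetic technique would you prefer if you had to be injected again".

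Under Hypotheses, the first aim reads "Any of the analgesic methods improves pain control respect to not utilizing any of them" and the second "Our second aim is to evaluate if any of the analgesic methods evaluated achieves a better pain control than the others". The analysis is a Friedman test, after which "paired comparisons were performed between each non-invasive anesthetic method with a Wilcoxon test". A Mann-Whitney test compares the sexes. No interval for a paired difference is named.

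**The concern.** Blinding the analyst does not protect an outcome that the subject scores. A subject who feels cold, vibration or a numbing cream on one zone and nothing on another may report less pain partly because less pain is expected. If so, a significant difference from control mixes analgesia with expectation. A comparison between techniques could be affected too, if one raises higher hopes than another.

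The sample size sharpens the worry. With 100 subjects, each serving as their own control, even small differences reach significance. A p-value does not show whether a difference is small enough for a modest expectation effect to explain it. Both aims rest on these scores, and a reader could take the blinding label to cover the subjects.

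**Working it through.** **Inputs from the documents.** Control-zone variance 2.69; planning difference 1 (called a precision, read here as one VAS point); 95% confidence; power 0.9; 46 subjects estimated; 100 analysed; no withdrawals.

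**Assumptions, because the documents give no figure.** Within-subject correlation r of 0 to 0.7; the same variance in all zones; an expectation shift b of 0.3 to 1.0 points.

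**1. The plan's own figure.** For two independent means, one-sided: n = 2 × 2.69 × (1.645 + 1.282)² / 1² ≈ 46.07. This agrees with the stated 46; the two-sided version gives 57. The figure does not bear on blinding, but it confirms the reading of the variance and of the 1-point difference.

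**2. Smallest significant difference in one paired contrast.** SE = √(2 × 2.69 × (1 − r) / 100).
- r = 0: SE = √0.0538 = 0.232; 1.96 × SE = 0.455
- r = 0.5: SE = √0.0269 = 0.164; 1.96 × SE = 0.321
- r = 0.7: SE = √0.01614 = 0.127; 1.96 × SE = 0.249

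The threshold is under half of the planning difference.

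**3. Chance that an inert technique is significant against control.** For a single contrast: Φ(b/SE − 1.96) + Φ(−b/SE − 1.96). For b = 0.5 and r = 0 this is Φ(2.156 − 1.96) + Φ(−4.116) ≈ 0.578. For the planned sequence (Friedman p < 0.05, then Wilcoxon p < 0.05), 1,500 simulated trials used four equally correlated normal zones, an assumed control mean of 5, scores clipped to 0–10, and the same shift in all three techniques. Control pairs were taken to be among the Wilcoxon comparisons, because the first hypothesis needs them.

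| Assumed shift | Analysis | r = 0 | r = 0.5 | r = 0.7 |
|---|---|---|---|---|
| 0.3 | single contrast | 25% | 45% | 66% |
| 0.3 | planned sequence | 12% | 26% | 42% |
| 0.5 | single contrast | 58% | 86% | 98% |
| 0.5 | planned sequence | 36% | 72% | 94% |
| 1.0 | single contrast | 99% | >99% | >99% |
| 1.0 | planned sequence | 97% | 100% | 100% |

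A repeat with 1,000 simulated trials agreed to within four percentage points.

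**4. Technique against technique.** If all three techniques carry the same shift, significance between two inert techniques stays at about 2% to 6%. It rises to about 55%, 83% and 97% (r = 0, 0.5, 0.7) only when expectation is assumed to differ by 0.5 points (shifts 0.5, 0.5 and 1.0).

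**5. What an interval would add.** Write the expected difference as d = t + b, with t the analgesic effect and b the expectation shift. At r = 0.5 an observed d of 1 gives 1 ± 0.321, or 0.679 to 1.321. The interval is the same for t = 1, b = 0 as for t = 0.5, b = 0.5, so it cannot separate the two. Its limit nearer zero is the uniform shift that would just remove significance in that contrast. With the Wilcoxon test this holds exactly only for an interval obtained by inverting that test, and it ignores the preceding Friedman test, which step 3 shows to matter (25% falls to 12% at 0.3 points and r = 0).

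**6. What the hypothesis asks.** The first hypothesis compares each technique with using none. That is the total effect of applying the technique, t + b. No sentence in the plan claims an effect free of expectation or compared with a sham.

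**The case for a change.** The strongest case for a change is that it would cost almost nothing. Two sentences would say who was blinded and list expectation as a limitation. Paired differences with 95% intervals could be computed from existing data. Without them, the label may be read as covering the subjects, and a bare p-value does not tell a 0.3-point difference from a much larger one. Nor does this case ask for masking, so the difficulty of masking vibration or cold is no answer to it.

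Much of this stands. The label is incomplete, the procedures make masked subjects implausible, and no interval is named. An estimate with an interval is good reporting practice, and a Hodges-Lehmann paired difference with an interval from the signed-rank test, marked as post hoc, would be a sensible choice.

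It does not amount to a defect in the plan. The statistical paragraph speaks of average results and average pain by technique, so the size of differences is already in view, although the plan does not promise to report it. The 1-point planning difference is a sample-size input and gives no yardstick for expectation. The percentages in step 3 follow from assumed shifts; they show that 100 paired subjects detect small differences, whatever their cause. The risk to the second aim needs expectations that differ between techniques. That is possible, but nothing in the documents indicates it.

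**Conclusion.** No change to the plan. That only the analyst is shown as blinded is correct, and so is the threshold of about 0.25 to 0.46 points, given variance 2.69 in every zone, 100 subjects and a correlation of 0 to 0.7. The chance that expectation alone yields a significant difference from control runs from 12% to 100% under the planned sequence, depending entirely on an assumed shift of 0.3 to 1.0 points and on that correlation. It is a sensitivity range and gives no evidence that such bias occurred.

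An untreated comparator is a fair trade-off for a question about using a technique or not. A sham would answer a different question and could not be added after the final analysis of 30/04/2019. Who was blinded is a missing detail that the report can supply. A limitation sentence leaves the technique-versus-nothing conclusion as it is, and added intervals would neither measure nor remove expectation. No test, result or stated conclusion would alter.
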